## **4            INVESTIGATIONAL PLAN**

### **4.1            Study Design and Duration**

This is a randomized placebo-controlled double-blind study for the 16 weeks, in patients with SLE whose active lupus manifestation is primarily arthritis. The study consists of a baseline visit, a 16-week treatment period (with visits every 4 weeks), and a telephone follow up 8 weeks after the last dose of study drug. Patients are expected to participate in the study for up to approximately 26 weeks (including screening visit).

Informed consent will be obtained at the Screening Visit, prior to patients undergoing any study procedures. Eligibility criteria will be assessed and medical history will be reviewed prior to Protocol Amendment 1, November 30, 2015

patient's participation in this study. Starting at the baseline visit, patients will receive 125 mg sc of abatacept or placebo every week for 16 weeks. Patients may continue on their stable background standard of care medications (according to the protocol) throughout the study. In the first dose visit, patients will be monitored for systemic symptoms for at least 1 hour after abatacept has been administered.

Subjects who discontinue the trial early, i.e. prior to Week 16 should come to a follow-up study completion visit within 1 week of treatment termination.

Unscheduled visits for safety or for any other reason may be conducted at any time during the study.

During the study period, at 4 week intervals, swollen and tender joint counts (28 joints), the British Isles Lupus Assessment Group (BILAG) score, SLE Disease Activity Index (SLEDAI 2K), Physician Global Assessment Score and Patient Global Assessment will be assessed in addition to routine safety laboratory and physical tests. Disease related immunology tests/biomarkers will be taken at baseline and 16 weeks.

Bilateral Posterior-Anterior (PA) Hand X-rays (including wrists) will be performed at baseline for all subjects. Ultrasound examination of the PIP (2-5), MCP (2-5), and wrist joints designated below will be performed at baseline and at 16 weeks. At baseline and 16 weeks, synovitis (18 joints), tenosynovitis and erosions will be assessed.

Please see Time and Events Schedule in Section 6.

SLE patients with 3 or more swollen and tender joints and moderate or severe lupus activity (SLEDAI 2K score 4 or greater) will be eligible for this study. In addition, patients must have current or historical documented positive Antinuclear Antibody (ANA) and/or anti-double stranded deoxyribonucleotide antibody (anti-dsDNA).

The established SLE therapy (as allowed by the study) at study entry will be continued as background therapy. Background therapy should be kept stable throughout the study, although increase in prednisone to not more than 30 mg a day, which much be tapered to  $\leq 10$  mg daily by 8 weeks, will be permitted. Tapering of prednisone dose at any time will be permitted. Dosage increases in antimalarial, or any other non-glucocorticoid immunosuppressives, or introduction of any of these or a biologic agent as a new therapy (not allowed by the protocol) will be regarded as a treatment failure. Subjects requiring prednisone or equivalent doses  $>10$  mg a day at/after the 8 week visit will be regarded as treatment failures.

The US will be performed by a rheumatologist with expertise in musculoskeletal ultrasound and images will be digitally saved. US will be performed at UCLA only, for the 32 patients enrolled there. Each UCLA patient will have ultrasounds performed on the same machine by the same ultrasonographer at baseline and 16 weeks.

18-Joint US Scoring System (bilat wrists, bilat MCPs 2-5, bilat PIPs 2-5)

JOINT	VIEW	Power Doppler Synovitis	B-mode Synovial Hypertrophy	Tendons	Erosions
Wrists	Dorsal Longitudinal Midline (Radio carpal, intercarpal)	X	X		
MCPs (2-5)	Dorsal Orthogonal	X	X		X (MCP 1,2, and 5)
	Volar Longitudinal	X	X	X	
	Dorsal Paratendon	X	X	X	
PIP/IP (2-5)	Volar Longitudinal	X	X	X	

US assessments will be performed using the 18-joint US score. To date, no single US scoring system has been determined as the prevailing method. However, several US scoring systems have demonstrated that power Doppler synovitis and B-mode synovial hypertrophy scores are sensitive to change. For this proposal, selection of the specific 18 joints was based on maximizing precision, reliability, and feasibility for ultrasonography. Most US scoring systems weigh heavily on the hands and wrists. Some studies demonstrate the presence of normal amounts of fluid at the 1st metatarsophalangeal (MTP) joints primarily as well as with 2-5 MTPs. In addition, these joints frequently demonstrate the presence of deformities such as hammer toes. Thus, these joints were excluded. Grey-scale synovial hypertrophy and power doppler will be assessed for bilateral wrists (dorsal), MCPs 2-5 (dorsal and volar), and PIPs/IPs 2-5 (volar). In addition, MCP 2, and 5 will be assessed for erosions. All the above areas will be examined with B-Mode and power Doppler mode sonography (Table above). Standard OMERACT definitions will be used for effusion and synovial hypertrophy.

Assessment of the extensor and flexor tendons (grey-scale and power doppler) of the MCPs bilaterally will be obtained as well for further exploratory analyses.

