Inclusion Criteria	
 
1. Meet at least 4 of the 11 American College of Rheumatology (ACR) 1997 criteria for classification of SLE (see Appendix 1). OR meet the recent classification recommended by SLICC (Appendix 2)
 
2. <math>\geq 3</math> swollen and tender joints on 2 examinations at least 2 weeks apart and no more than 8 weeks apart.
 
3. SLEDAI2K score <math>\geq 4</math> indicating active disease.
 
4. Documented positive ANA (<math>\geq 1:80</math>) and/or anti-dsDNA during course of SLE.
 
5. Men and women, at least 18 years of age. Women of childbearing potential must use adequate method(s) of contraception to avoid pregnancy throughout the study and for up to 2 months after last study drug dose. They must have a negative serum or urine pregnancy test prior to the start of study medication.
 
6. Background therapies allowed: antimalarials (dose constant for <math>\geq</math> one month before study entry and during 16 weeks of trial), methotrexate (same criteria as for antimalarials), azathioprine (same criteria), mycophenolate (same criteria), leflunomide (same criteria). During the screening period and for up to 6 weeks after randomization, a daily prednisone (or equivalent) regimen of up to 20 mg daily may be initiated to treat the moderate to severe disease activity present at screening. The initial steroid regimen is not required if investigators or patients believe that the risks would outweigh the potential benefits. Patients who do not take any glucocorticoids during the study will be included in the treatment groups and analysis.
 
 
*Steroids should be tapered to a target dose of no more than 10 mg/day of prednisone (or equivalent) by the end of Week 8 (Day 56). The steroid regimen should be tapered as quickly as safely possible. Prednisone dose requirements higher than 10 mg daily at the 8 week visit will cause the patient to be ruled a non-responder for the abatacept treatment arm.

---------------------------	--

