## **4.3 Concomitant Treatments**

### ***4.3.1 Prohibited and/or Restricted Treatments***

Initiation of therapy with any of the following medications or treatments during the study is not allowed:

- Methotrexate
- Azathioprine
- Cyclophosphamide
- Leflunomide
- Rituximab
- Belimumab
- Cyclosporine
- Tacrolimus
- Gammaglobulin
- Experimental therapies for treatment of SLE
- Plasmapheresis
- Prednisone or equivalent at doses >20 mg daily.

The prescribing label of all concomitant medications used as subject's background therapy should be evaluated by the investigator for continued administration during subject's participation in this study (e.g. known toxicities, drug-drug interactions).

Change in SLE standard of care (SOC) therapy after 12 weeks will not be permitted to allow assessment of efficacy of abatacept.

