#### **5.5 Concomitant Treatments**

##### ***5.5.1 Prohibited and/or Restricted Treatments***

The following medications are prohibited throughout the 24 week study period:

- Any biologic DMARD (such as but not limited to: anakinra, infliximab, etanercept, adalimumab, rituximab, belimumab or any other investigational biologic).
- Live vaccines.
- Use of any investigational drug other than study medication.
- Corticosteroid use higher than the equivalent of prednisone 10 mg/day is not permitted after week 8.

The following rescue medications may be used:

- Nonsteroidal antiinflammatory drugs (NSAIDS) or Aspirin
- Acetaminophen
- Combination products, including acetaminophen and narcotic analgesics (eg, acetaminophen with codeine phosphate or propoxyphene napsylate or oxycodone hydrochloride or hydrocodone bitartrate).
- Tramadol
- Morphine.
- Prednisone at doses not to exceed 20 mg a day in the first 4 weeks of the study, but not more than 10 mg daily after 8 weeks

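### Section 4.1 allows prednisone up to 30 mg/day on study where four other sections stop at 20 mg, and Section 4.2.3 holds prednisone at baseline dose against the week-8 taper

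*Combined protocol and SAP*

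**What the plan says.** **Ceiling.** Section 4.1 asks for stable background therapy but makes an exception for an "increase in prednisone to not more than 30 mg a day", to be brought down to 10 mg or less by 8 weeks. Four other places set a lower ceiling:

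- Synopsis, inclusion criterion 6, as an optional starting regimen: "During the screening period and for up to 6 weeks after randomization, a daily prednisone (or equivalent) regimen of up to 20 mg daily".
- Section 4.2.3: a rescue increase in prednisone may not go above 20 mg daily.
- Section 4.3.1, among treatments that may not be initiated during the study: "Prednisone or equivalent at doses >20 mg daily".
- Section 5.5.1, rescue medication: "Prednisone at doses not to exceed 20 mg a day in the first 4 weeks of the study", and not above 10 mg after 8 weeks.

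The entry exclusions in the Synopsis and Section 4.2.1 also use 20 mg. The one other place with 30 mg is exclusion (o) in Section 4.2.1, on concomitant illness likely to need more than 30 mg/day.

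**Hold or taper.** Section 4.2.3 names prednisone, with MMF, leflunomide and hydroxychloroquine, as background treatment to stay at its baseline dose for the whole study. The Synopsis says "Steroids should be tapered to a target dose of no more than 10 mg/day of prednisone (or equivalent) by the end of Week 8". Section 4.1 adds "Tapering of prednisone dose at any time will be permitted", and its sentence on patients who require more than 10 mg ends "mg a day at/after the 8 week visit will be regarded as treatment failures". Section 5.5.1 states: "Corticosteroid use higher than the equivalent of prednisone 10 mg/day is not permitted after week 8".

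**Where steroid dose is an outcome.** The Synopsis and the secondary objectives in Section 2 define steroid sparing by whether prednisone can be brought down to about 10 mg/day by week 16. Section 6.4.2 defines it by daily dose at baseline and week 16 and by cumulative dose over the 16 weeks.

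**The concern.** These are working dosing instructions for two sites planned to enrol 32 patients each. If one site works from Section 4.1 and the other from Section 4.3.1 or 5.5.1, early steroid exposure can differ by site. The same 25 mg dose could also be logged as compliant at one site and as a deviation at the other. The protocol itself treats the disputed range as more than a detail: its BILAG description and its live-vaccine precautions both place high-dose steroid above 20 mg/day.

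The sentence in 4.2.3 is a second, smaller problem. Read literally, it tells a site to hold a dose that the week-8 rules say must come down, in a trial where reducing that dose is a listed outcome.

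**Working it through.** The plan gives no cumulative steroid figure, so there is none to reproduce. The check is a side-by-side reading, followed by an illustration of scale.

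**1. Do the ceilings govern different acts?** No. Section 4.1 covers an increase during the study, and the rescue sentence in 4.2.3 covers the same act with a lower limit. Take a patient raised to 25 mg in week 2. The dose is within 4.1 (25 ≤ 30) and outside 4.2.3 (25 > 20), and it falls in the range listed in 4.3.1. No text says which section prevails. A patient who never exceeds 20 mg satisfies every ceiling.

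**2. Can the hold and the taper both be followed?** It depends on the entry dose, which may be up to 20 mg.

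| Entry dose | Dose at Day 56 if held | Above the 10 mg limit by | Change in daily dose to week 16 if held |
|---|---|---|---|
| 10 mg or less | unchanged | 0 | 0 |
| 15 mg | 15 mg | 15 − 10 = 5 mg/day | 0 |
| 20 mg | 20 mg | 20 − 10 = 10 mg/day | 0 |

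Only entrants above 10 mg meet a contradiction. For them the 4.2.3 sentence stands against three provisions: the Synopsis target, the mandatory taper in 4.1 and the prohibition in 5.5.1. Those three agree, so 4.2.3 is the sentence to change.

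**3. What could the ceiling difference amount to for one patient?** Assumptions, none of them from the plan: the patient takes the ceiling dose C on Day 0, tapers in a straight line to 10 mg over T days, then takes 10 mg/day to Day 112 (16 × 7).

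Cumulative dose = (C + 10)/2 × T + 10 × (112 − T)

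| T | C = 30 | C = 20 | Difference |
|---|---|---|---|
| 14 days | 20 × 14 + 980 = 1260 mg | 15 × 14 + 980 = 1190 mg | 70 mg (5.9%) |
| 28 days | 20 × 28 + 840 = 1400 mg | 15 × 28 + 840 = 1260 mg | 140 mg (11.1%) |
| 56 days | 20 × 56 + 560 = 1680 mg | 15 × 56 + 560 = 1400 mg | 280 mg (20.0%) |

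The difference is 5 mg × T. The last row uses the whole time allowed, although the Synopsis asks for the fastest safe taper, so it is an upper illustration for this taper shape. The documents do not say how many patients will take more than 20 mg, or enter on more than 10 mg, so no group figure can be given.

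**The case against.** The best defence concerns 4.2.3. Its sentence is a general one about background drugs, in a section on discontinuation, and the same paragraph allows a prednisone increase. It is hardly a strict dose freeze. Section 4.1 shows how rule and exception are meant to fit, and holding 15 or 20 mg to week 16 would require a site to ignore three specific limits. This stands: the hold sentence is the lesser fault. It still needs correcting, because unlike 4.1 it states no taper exception.

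It is also fair that the 20 mg provisions are not one uniform rule. They cover an optional initial regimen for up to 6 weeks, rescue, initiation of therapy, and the first 4 weeks. Exclusion (o) shows that 30 mg is not a lone slip. Taking 20 mg as the intended ceiling is therefore an inference from the weight of the text. But exclusion (o) screens for other illness and does not authorise a dose, so it does not remove the conflict.

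A reader might go further and infer any of the following. The documents do not support them.

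- *Held patients automatically become failures or non-responders.* Section 4.1 speaks of patients requiring more than 10 mg, and the Synopsis of dose requirements. A patient kept there by instruction is not clearly covered. The Synopsis non-responder sentence also names only the abatacept arm.
- *Held patients tell us nothing about steroid sparing.* Their change in daily dose would be fixed at zero by instruction, but they still contribute a cumulative dose under Section 6.4.2.
- *The primary comparison is biased.* Treatment is randomised and blinded, and the dose ceilings do not differ by arm. Every taper rule reaches 10 mg or less by week 8, eight weeks before the primary assessment. Nothing in the documents yields a between-arm difference.

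**Conclusion.** The point holds as an inconsistency in the dosing instructions. The main part is the ceiling: doses above 20 and up to 30 mg/day are both allowed and barred, with their deviation status undefined. The secondary part is the baseline-dose sentence in 4.2.3, which cannot be followed together with the week-8 limit by patients entering on more than 10 and up to 20 mg, and which does not fit the steroid-sparing outcome.

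What is affected is early steroid exposure, consistency between the two sites, and deviation classification. The ceiling difference is at most 10 mg/day. The 70 to 280 mg range for one patient's total depends on the assumed starting dose and taper shape and is not an estimate for the trial. The correction should be made, but nothing here shows that the efficacy conclusion would change.

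**What to change.** 1. In Section 4.1, change the ceiling from 30 to 20 mg/day. In exclusion (o) of Section 4.2.1, change the threshold from more than 30 to more than 20 mg/day. If the sponsor in fact intends 30 mg, the four 20 mg provisions must change instead; either way there should be one number.
2. In Section 4.2.3, remove prednisone from the list of drugs kept at baseline dose and refer to the taper to no more than 10 mg/day by Day 56.

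Two optional clarifications: say in 4.2.3 that rescue above 10 mg is limited to the period before week 8, and state in 5.5.1 the limit for weeks 4 to 8, which it currently leaves open.

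The cost is a few wording changes in one amendment. Sample size, visits and data collection are unaffected.

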## **4.2 Study Population**

For entry into the study, the following criteria MUST be met. Any exceptions must be approved by the Principal Investigator and/or IRB/IEC before enrollment.

### **4.2.1 Inclusion Criteria**

#### **1) Signed Written Informed Consent**

- a) Before any study procedures are performed, subjects will have the details of the study described to them, and they will be given a written informed consent document to read. Then, if subjects consent to participate in the study, they will indicate that consent by signing and dating the informed consent document in the presence of study personnel.

#### **Target Population**

- b) SLE as defined by meeting at least 4 of the 11 classification criteria of the American College of Rheumatology for the classification of Systemic Lupus Erythematosus. The 4 criteria need not be present at the time of study entry.

OR

Patients meet the new SLICC criteria for SLE. Patients must fulfill at least 4 criteria, including at least one clinical and one immunologic. Clinical criteria are acute cutaneous lupus, chronic cutaneous lupus, oral or nasal ulcers, nonscarring alopecia, synovitis (2 or more joints with swelling, or tenderness in 2 or more plus at least 30 min of morning stiffness), serositis, renal disease, neurologic, hemolytic anemia, leucopenia or lymphopenia, thrombocytopenia. Immunologic criteria are ANA above laboratory reference range, anti-dsDNA, anti-Sm, antiphospholipid, low complement and direct Coomb's test.

- c) Active arthritis, as defined by:

- 1) At least 3 or more swollen and tender joints
- 2) Moderate or severe lupus activity - SLEDAI 2K score 4 or greater
- d) Patients must have documented positive Antinuclear Antibody (ANA) and/or anti-double stranded deoxynuclear antibody (anti-dsDNA). Presence/absence of anti-CCP and rheumatoid factor will be measured but results will not exclude patients from the trial.
- e) No active nephritis, active central nervous system disease, or other life-threatening manifestations of SLE

#### **Age and Sex**

- f) Men and women,  $\geq 18$  years of age
- g) Women of childbearing potential (WOCBP) must use highly effective methods of birth control [for up to 4 weeks after the last dose of abatacept] to minimize the risk of

pregnancy. WOCBP must follow instructions for birth control for the entire duration of the study including a minimum of 28 days after dosing has been completed.

- Acceptable methods of highly effective birth control include:
  - Condom with spermicide
  - Hormonal contraceptives
  - Diaphragm and spermicide
  - Cervical cap and spermicide
  - Intrauterine device

Women must have a negative serum or urine pregnancy test (minimum sensitivity 25 IU/L or equivalent units of HCG) within 48 hours prior to the start of investigational product.

c) Women must not be breastfeeding

Sexually active fertile men must use highly effective birth control if their partners are WOCBP. Men that are sexually active with WOCBP must follow instructions for birth control for the entire duration of the study and a minimum of 28 days after dosing has been completed.

d) Women who are not of childbearing potential (ie, who are postmenopausal or surgically sterile; see Section 3.3.3 for the definition of WOCBP) and men may be included in the study.

e) Exclusion Criteria

Individuals to be excluded if:

- a) WOCBP who are **unwilling or unable** to use an acceptable method to avoid pregnancy for the entire study period and for at least 4 weeks after the last dose of study drug.
- b) Women who are pregnant or breastfeeding.
- c) Women with a positive pregnancy test on enrollment or before administration of abatacept.
- d) Sexually active fertile men not using effective birth control if their partners are WOCBP.

**Medical History and Concurrent Diseases**

- e) Subjects who are impaired, incapacitated, or incapable of completing study-related assessments.
- f) Subjects with current symptoms of severe, progressive, or uncontrolled renal, hepatic, hematologic, gastrointestinal, pulmonary, cardiac, neurologic, or cerebral disease,

whether or not related to SLE and which, in the opinion of the investigator, might place a subject at unacceptable risk for participation in the study.

- g) Female subjects who have had a breast cancer screening that is suspicious for malignancy and in whom the possibility of malignancy cannot be reasonably excluded by additional clinical, laboratory, or other diagnostic evaluations.
- h) Subjects with a history of cancer in the last 5 years, other than non-melanoma skin cell cancers cured by local resection, or carcinoma in situ. Existing non-melanoma skin cell cancers should be removed, the lesion site healed, and residual cancer ruled out before administration of the study drug.
- i) Subjects who currently abuse drugs or alcohol.
- j) Subjects with evidence (as assessed by the investigator) of active or latent bacterial or viral infections at the time of potential enrollment, including subjects with evidence of human immunodeficiency virus (HIV), hepatitis B or hepatitis C detected at any time prior to screening for this study
- k) Subjects with herpes zoster or cytomegalovirus (CMV) that resolved less than 2 months before the informed consent document was signed.
- l) Subjects who have received any live vaccines within 3 months of the anticipated first dose of study medication.
- m) Subjects with any serious bacterial infection within the last 3 months, unless treated and resolved with antibiotics, or any chronic bacterial infection (eg, chronic pyelonephritis, osteomyelitis, or bronchiectasis).
- n) Subjects at risk for tuberculosis (TB). Specifically excluded from this study will be subjects with a history of active TB within the last 3 years, even if it was treated; a history of active TB greater than 3 years ago, unless there is documentation that the prior anti-TB treatment was appropriate in duration and type; current clinical, radiographic, or laboratory evidence of active TB; and latent TB that was not successfully treated ( $\geq 4$  weeks).
- o) Subjects with concomitant illness that in the opinion of the investigator, is likely to require additional high dose oral glucocorticosteroid therapy (i.e.  $>30$  mg prednisone or equivalent per day) during the study (e.g. severe asthma)

